Full study protocol and statistical analysis plan

Official Title of the study:

Endothelial cell-specific-molecule-1 (endocan) levels in women with premature ovarian insufficiency

Date of the document:

July 2018.

Contents:

- 1. Participant Flow
- 2. Baseline Characteristics
- 3. Outcome Measures
- 4. Endpoints of the study
- 5. Limitations and Strengths
- 6. Certain Agreements
- 7. Results Point of Contact

1. Participant Flow

Recruitment Details

This was an observational prospective cohort study conducted at Obstetrics and Gynecology Department of Cengiz Gokcek Obstetrics and Children's Hospital between July and December 2018. Seventy-seven women were enrolled in the study in two groups. We consecutively recruited 38 subjects with idiopathic POI, and 39 healthy patients were selected for the control group. All patients gave their oral and written informed consent before their inclusion in the study.

Pre-assignment Details

We firstly will assess the recruited people to ensure meeting the inclusion and exclusion criteria. The inclusion criteria are made according to the official documents.

Arm/Group Information *

There are two groups in the study.

Arm/Group Title *

POI group = Group A Control group= Group B

2. Baseline Characteristics

In two groups (poi - control), the total number of individuals required to find a statistically significant effect size expectation was calculated as 72 (α =0.05, 1- β =0,80) in terms of endocan measurements. The normality of distribution of continuous variables was tested using the Shapiro-Wilk test. To compare numerical variables between 2 groups, Student's t-test (for normal data) or the Mann-Whitney U test (for non-normal data) was performed. The Chi-square test was used to assess the relationship between categorical variables, and Spearman's rank correlation coefficients were used to assess the relationship between non-normal numeric data. Frequency, percentage (%) and mean ± standard deviations (mean ± SD) are given as descriptive statistics. Statistical analysis was performed using the SPSS for Windows version 24.0 software package, and p valued < 0.05 were accepted as statistically significant.

3. Outcome Measures

At enrollment, for both groups, we collected data about age, height, weight, BMI, age of menarche, obstetrics history, history of smoking, regular exercise and family history of POI. We defined that POI period is a time from diagnosis to admission. At enrolment, all patients underwent vaginal ultrasonography for the assessment of antral follicle count (AFC) and venous blood sample from the antecubital veins for measuring serum concentration of Endocan, Follicle-stimulating hormone (FSH), E2, anti-mullerian hormone (AMH) and complete blood count (CBC). In control subjects venous blood samples and AFC were collected during the early follicular phase of the menstrual cycle (2nd to 5th days) in the morning (between 08.00 and 09.00 h). In the POI group, measurements were repeated with 4-week intervals. AMH was not measured in the control group. AFC were assessed through vaginal ultrasonography by the same author. Blood samples were separated by centrifugation for 10 minutes at 1500 g after clotting for 30 minutes at room temperature. The serum samples were subsequently stored in aliquots at -80°C prior to the analysis of endocan. The serum endocan level was

measured using a commercially available enzyme-linked immunosorbent assay (ELISA) kit, which is produced to detect human endocan levels with high sensitivity and specificity. The endocan measurements were performed in accordance with company's protocol. The kit uses the sandwich ELISA principle. A biotinylated detection antibody specific for human ESM1 (endocan) and avidin-horseradish peroxidase conjugate were used in the measurement. Spectrophotometry at a wave length of 450 ± 2 nm was used in the detection of optical density, which is proportional to the concentration of human endocan level. The intra- and inter-assay variation coefficients were 6.36% and 6.09%, respectively.

4. Endpoints of the study:

The primary endpoint in this analysis was to compare endocan levels in POI group and control group. The secondary endpoint was to compare endocan levels in POI group for POI period. Tertiary endpoint was to compare the endocan levels in both groups according to the births.

5.Limitations and strengths:

There are strengths of this study. The women participating in the study had idiopathic POI without any treatment. The women who have not taken any hormonal treatments, alternative and complementary treatments that may have possible potential effects on endocan levels.

6. Certain Agreements

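### The primary endocan comparison is unadjusted in a non-randomised study, although age, smoking, BMI and exercise are recorded in both groups

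*Combined protocol and SAP*

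**What the plan says.** Section 1 (Recruitment Details) describes the design as observational: "This was an observational prospective cohort study conducted at Obstetrics and Gynecology Department". The two groups were formed in different ways: "We consecutively recruited 38 subjects with idiopathic POI, and 39 healthy patients were selected for the control group". No source, selection procedure or matching rule for the controls is given, and eligibility is referred elsewhere: "The inclusion criteria are made according to the official documents".

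Section 4 defines the primary endpoint: "The primary endpoint in this analysis was to compare endocan levels in POI group and control group". Section 2 supplies the method: "To compare numerical variables between 2 groups, Student's t-test (for normal data) or the Mann-Whitney U test (for non-normal data) was performed". Besides this, it lists Shapiro-Wilk, chi-square, Spearman correlation and descriptive statistics. None of these adjusts a group comparison for a third variable.

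Section 3 lists what is recorded at enrolment in cases and controls alike: "we collected data about age, height, weight, BMI, age of menarche, obstetrics history, history of smoking, regular exercise and family history of POI".

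On sample size, section 2 says that "the total number of individuals required to find a statistically significant effect size expectation was calculated as 72", at alpha 0.05 and power 0.80. It gives no effect size, SD or sidedness.

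**The concern.** Without randomisation, nothing in the design makes the two groups alike in age, smoking, BMI or activity. Consecutive cases and controls chosen by an undescribed route may differ on any of them. If such a variable is also related to endocan, the difference in means mixes its contribution with that of POI, and neither the t-test nor the Mann-Whitney test can separate the two. Testing the covariates between groups may reveal an imbalance but does not remove it from the endocan comparison.

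The primary conclusion rests on this single comparison, and the bias could go either way. The plan itself accepts that endocan may respond to other factors: section 5 counts it as a strength that the women had taken no treatments that might affect it.

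**Working it through.** **Inputs from the document.** n = 38 POI and 39 controls (section 1). Total N = 72, alpha 0.05, power 0.80 (section 2).

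**Assumed, because the document does not give them.** Two-sided testing; the correlation r of one covariate with endocan within groups; the systematic group difference g in that covariate, in SD units.

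**1. Effect size behind N = 72.** The stated figure cannot be reproduced forwards without an effect size, so it is solved backwards. For a two-sided t-test with 36 per group (df = 70), 80% power is reached at d = 0.670. A one-sided test would give d = 0.59. At the enrolled 38/39, power for d = 0.670 is 0.826.

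**2. Bias.** Unadjusted bias in SD units = r × g. The smallest case is 0.2 × 0.5 = 0.10; the largest is 0.4 × 1.0 = 0.40. As a share of 0.67, these are 0.10/0.67 = 15% and 0.40/0.67 = 60%.

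**3. Rejection rate with no POI effect.** The t statistic is noncentral t with 75 df and noncentrality r × g × √(38 × 39/77) = r × g × 4.387. For example, 0.40 × 4.387 = 1.755. The critical value is 1.992. The Mann-Whitney figures are simulated on lognormal data, 8,000 runs per setting.

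| r | g (SD) | bias (SD) | t-test rejects | Mann-Whitney rejects |
|---|---|---|---|---|
| 0.2 | 0.5 | 0.10 | 7.2% | 7.1% |
| 0.2 | 1.0 | 0.20 | 13.9% | 14.2% |
| 0.3 | 0.5 | 0.15 | 10.0% | 10.1% |
| 0.3 | 1.0 | 0.30 | 25.5% | 24.0% |
| 0.4 | 0.5 | 0.20 | 13.9% | 13.2% |
| 0.4 | 1.0 | 0.40 | 41.0% | 39.0% |

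With smaller values (r = 0.1 to 0.2, g = 0.2 to 0.3), bias is 0.02 to 0.06 SD and the t-test rejects 5.1% to 5.8% of the time. With no systematic imbalance, the unadjusted test rejected 4.9% to 5.4% in simulation, so it holds its level. An adjusted model rejected 4.8% to 5.3% throughout; that follows by construction, because the only confounder was measured and correctly modelled.

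**4. Masking.** True d = 0.67, imbalance in the opposite direction, 6,000 runs per setting:

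| r | g (SD) | unadjusted power | adjusted power |
|---|---|---|---|
| 0.2 | 0.5 | 70% | 81% |
| 0.2 | 1.0 | 54% | 74% |
| 0.3 | 0.5 | 62% | 84% |
| 0.3 | 1.0 | 36% | 75% |
| 0.4 | 0.5 | 53% | 86% |
| 0.4 | 1.0 | 22% | 80% |

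The noncentral t at d = 0.67 − r × g gives unadjusted power of 69% in the mildest case and about 21% in the most severe, in line with the simulation.

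**5. What adjustment does to power.** With k covariates, N = 77 and squared standardised imbalance D², the variance of the group coefficient is multiplied by 1 + (D² × 38 × 39/77 + k)/(N − k − 3). The residual SD becomes √(1 − R²), and df = N − 2 − k. For k = 2 and D² = 1.0, the factor is 1 + (19.25 + 2)/72 = 1.295. For k = 4 it is 1 + (19.25 + 4)/70 = 1.332. Over D² = 0 to 1.0 and R² = 0.05 to 0.25, power at d = 0.67 is 0.743 to 0.910 with two covariates and 0.731 to 0.902 with four, against 0.826 unadjusted. At R² = 0 and D² = 1.0 it falls to 0.72 and 0.71.

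**The case against.** The strongest reply is that the size of the problem is entirely assumed. The documents report no group difference in any covariate and no association with endocan, and small values are as consistent with them as large ones; the 41% and 22% figures need a correlation of 0.4 and a full 1 SD difference together. This stands as a limit on any claim about consequence. It does not touch the absence of an adjusted analysis.

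Second, the endpoint is worded as a comparison, and an unadjusted test is valid for a purely descriptive contrast between two groups. That is fair, but a difference between POI cases and healthy controls is of interest mainly for what it says about POI, and the descriptive result is kept under the fix.

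Third, matching or age restriction may be set out in the eligibility documents, which are not reproduced, and some restriction is visible: controls are healthy, and cases are idiopathic and untreated. Matching may indeed have been done. The plan does not say so, and the planned tests would take no account of it. Neither visible restriction balances age, smoking, BMI or exercise.

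Fourth, the tertiary endpoint compares endocan according to births, which can be read as a form of stratification. It is not the primary comparison and uses none of the four covariates.

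Finally, the covariate set is a judgement. The documents do not say that age or smoking affects endocan, and smoking history was taken at the same visit as BMI and exercise, so the argument that a variable recorded after diagnosis may be affected by POI could be extended to it. This stands in part: the investigators should give their causal reasons for the set they prespecify.

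**Conclusion.** The concern holds. As described, the only planned analysis of the primary endpoint is an unadjusted two-group test in a non-randomised study, while four plausible confounders are recorded in both groups and left unused. That conclusion comes from the text and does not depend on any figure.

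The size and direction of bias are unknown. Under the assumed values, the false-positive rate ranges from close to nominal when imbalance is small to about 41% at the upper end, and unadjusted power at d = 0.67 can fall from 83% to 22%. The d of 0.67 is itself inferred from N = 72 under a two-sided t-test. This should be fixed: it is a cheap improvement to the one analysis that carries the primary conclusion, not evidence that the result is wrong.

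**What to change.** Prespecify as the primary analysis a linear model of endocan on group, adjusted for age and smoking, with endocan log-transformed if residuals are skewed. Report the adjusted difference, or geometric mean ratio, with its 95% CI. Add BMI and regular exercise in a prespecified sensitivity model, since both were recorded after POI diagnosis and may be affected by it. State the causal reasoning for the covariate set. Keep the unadjusted test as supportive. Do not adjust for FSH, E2, AMH or AFC, which are part of the POI phenotype. Also state how controls were selected, and if they were matched, include the matching variables in the model.

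The cost is SAP wording and two regressions in the software already named, with no new data. The primary model spends about two degrees of freedom and the sensitivity model about four. Power may rise or fall: it drops to between 0.71 and 0.74 when groups are strongly imbalanced and the covariates predict endocan weakly or not at all, and rises to about 0.90 when groups are balanced and the covariates explain a quarter of the variance. Unmeasured confounding remains.

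### Student's t-test is the only test named for normal two-group data; if the POI-period or births comparisons become two-group splits unequal in size and variance, it will not hold 5%

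*Combined protocol and SAP*

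**What the plan says.** The statistical methods stand in section 2 (Baseline Characteristics). One rule covers two-group comparisons of numerical data: "To compare numerical variables between 2 groups", Student's "t-test (for normal data) or the Mann-Whitney U test (for non-normal data) was performed". The branch is chosen on normality alone: "The normality of distribution of continuous variables was tested using the Shapiro-Wilk test". Neither a check of variances nor an unequal-variance test appears. The significance rule is "p valued < 0.05 were accepted as statistically significant".

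Section 1 gives the sizes of the two main groups: "We consecutively recruited 38 subjects with idiopathic POI, and 39 healthy patients were selected for the control group".

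Section 4 lists two further endpoints. Within the POI group: "The secondary endpoint was to compare endocan levels in POI group for POI period". By obstetric history: "Tertiary endpoint was to compare the endocan levels in both groups according to the births". Neither has a cut-point, a number of categories, subgroup sizes or a test of its own. Section 3 defines POI period as a length of time. Section 2 also lists Spearman correlation for relationships between non-normal numeric variables.

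**The concern.** Student's test pools the two group variances. When the groups are about equal in size, unequal variances do little harm. When sizes and variances both differ, the pooled standard error is wrong. It is too small if the smaller group is the more variable, and too large if the larger group is.

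The near-balance of 38 and 39 comes from how POI women and controls were recruited. Nothing in the plan balances women by births or by POI period. Section 4 words both of these endpoints as comparisons, and the two-group rule is the only method listed for comparing a numerical variable; no method for three or more groups is given. A two-category split tested by that rule is therefore a natural reading, though not the only one. On that reading, the secondary and tertiary p-values could be too small or too large, and the reader could not tell which.

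**Working it through.** **The plan's own figure.** Section 2 gives a total of 72 at alpha 0.05 and power 0.80 ("effect size expectation was calculated as 72"). No effect size or SD is stated, so 72 cannot be reproduced. Solving backwards for 36 per group, two-sided, gives a standardised difference of 0.67. That figure concerns the primary comparison, and the choice between Student and Welch does not change it.

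**Inputs.** From the documents: 38 POI women, 39 controls, alpha 0.05 (taken as two-sided). Assumed, because the documents give none: the split sizes, the SD ratios and normal data.

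**Why size and variance interact.** For group sizes n1, n2 and SDs s1, s2:

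- True variance of the mean difference: V = s1²/n1 + s2²/n2
- Variance that Student's test estimates on average: P = [(n1−1)s1² + (n2−1)s2²]/(n1+n2−2) × (1/n1 + 1/n2)

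The t statistic is too widely spread if √(V/P) is above 1, and too narrowly if it is below 1.

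- 10 women with SD 2, 28 with SD 1: V = 4/10 + 1/28 = 0.4357. P = (9×4 + 27×1)/36 × (1/10 + 1/28) = 1.75 × 0.1357 = 0.2375. √(V/P) = 1.35.
- Reversed, 28 with SD 2, 10 with SD 1: V = 4/28 + 1/10 = 0.2429. P = (27×4 + 9×1)/36 × 0.1357 = 3.25 × 0.1357 = 0.4411. √(V/P) = 0.74.
- 38 with SD 2, 39 with SD 1: V = 4/38 + 1/39 = 0.1309. P = (37×4 + 38×1)/75 × (1/38 + 1/39) = 2.48 × 0.05196 = 0.1289. √(V/P) = 1.01.
- 19 vs 19: V = P exactly, whatever the SDs.

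**Type I error of Student's test.** Simulated with equal means, normal data and 200,000 data sets per setting. Each cell gives SD ratio 1.5 / ratio 2.

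| Split | Larger SD in smaller group | Larger SD in larger group |
|---|---|---|
| 38 vs 39 (primary) | 5.2% / 5.3% | not run |
| 19 vs 19 | 5.1% / 5.2% | same by symmetry |
| 17 vs 21 | 6.0% / 6.9% | 4.2% / 3.9% |
| 14 vs 24 | 7.8% / 9.7% | 3.1% / 2.3% |
| 10 vs 28 | 10.3% / 14.9% | 2.0% / 1.0% |
| 20 vs 57 (births, all 77) | 10.4% / 14.8% | 1.9% / 0.9% |

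Welch's test stays between 4.8% and 5.2% in every one of these settings. At 38 vs 39 with an SD ratio of 3, Student's error is 5.5%.

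**Does the plan's normality check help?** No. With the switch to Mann-Whitney on a failed Shapiro-Wilk test, the error at 10 vs 28 (larger SD in the smaller group, 6,000 data sets) is 10.1% at ratio 1.5 and 15.2% at ratio 2.

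**Power given up if variances are equal.** With the effect set so that Student's test has about 80% power at each split (20,000 data sets), Student and Welch give:

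- 38 vs 39: 80.6% and 80.6%
- 12 vs 26: 79.3% and 77.5%
- 10 vs 28: 79.3% and 75.9%

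**The case against.** The strongest reply is that the documents do not establish the situation in which Student's test fails. POI period is defined as a duration and births may be a count, so either could be analysed by Spearman correlation or in three or more categories. No two-sample t-test would then apply. Even with two groups, a median cut of the 38 POI women gives 19 vs 19 and almost no distortion. No SDs are given, so unequal variances are possible but not shown. The equal-variance reading itself rests on the name Student's: the text never states that equal variances are assumed, and SPSS prints the unequal-variance row by default. All of this stands, and it makes the point conditional.

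A reader might infer more than the documents support:

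- That Student's test governs every two-group comparison. It does not; non-normal data go to Mann-Whitney.
- That the POI-period and births splits are two-way and unbalanced. The plan does not say so. That nothing balances them does not show that they are lopsided.
- That the main conclusion is at risk. At 38 vs 39 it is not.
- That the lower-endpoint p-values are several times too liberal. That needs both a strongly lopsided split and roughly a twofold SD ratio, and the documents give neither.
- That reported error bars are wrong. The plan reports mean ± SD, which does not depend on the test, and specifies no confidence intervals.

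What the reply does not answer is that the plan leaves the splits open while naming a test whose validity depends on how they fall.

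**Conclusion.** The point holds in conditional form and is minor. It bears only on the secondary and tertiary endpoints. It applies only if those are run as two-group comparisons, the data pass the normality check, the groups differ in both size and variance, and the equal-variance result is the one reported. Under the assumed splits and SD ratios of 1.5 to 2, Student's error ranges from about 1% to 15%, and near-balanced splits stay close to 5%. The documents show no actual error in a planned result. They do show a default that can be replaced, at small cost, by one that holds 5% across all the settings tried.

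**What to change.** In section 2, replace Student's t-test with Welch's unequal-variance t-test for two-group comparisons of normal data, and report the mean difference with its Welch 95% confidence interval. Name Welch outright rather than testing variances first: a Levene switch added to the plan's rule still leaves 8.3% and 9.2% at 10 vs 28 (SD ratios 1.5 and 2, larger SD in the smaller group).

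**Cost.** A small change of wording, no new data and no change to the total of 72. If variances are in fact equal, power falls by about 0 points at 38 vs 39, 2 at 12 vs 26 and 3 at 10 vs 28.

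**What it does not cure.** The Mann-Whitney branch is untouched, and it too can depart from 5% when spreads differ: 7.4% and 9.4% at 10 vs 28 for normal data with SD ratios 1.5 and 2. Nor does the change affect any analysis of POI period or births by correlation. It also does not supply the missing definitions of the POI-period and births groups, which the plan should state in any case.

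### Does giving a clock-time window for blood draws in controls only undermine the endocan comparison?

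*Combined protocol and SAP*

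**What the plan says.** Section 3 (Outcome Measures) has three statements about when blood was taken.

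- For both groups, at enrolment: a "venous blood sample from the antecubital veins for measuring serum concentration of Endocan" and other analytes. No hour is given.
- For controls: "In control subjects venous blood samples and AFC were collected during the early follicular phase of the menstrual cycle", on days 2 to 5, "in the morning (between 08.00 and 09.00 h".
- For POI women: "In the POI group, measurements were repeated with 4-week intervals". This is an interval, again without an hour.

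Section 4 makes the group contrast primary: "The primary endpoint in this analysis was to compare endocan levels in POI group and control group". Section 2 names the method: "To compare numerical variables between 2 groups, Student's t-test (for normal data) or the Mann-Whitney U test (for non-normal data) was performed". Section 1 describes the groups: "We consecutively recruited 38 subjects with idiopathic POI, and 39 healthy patients were selected for the control group", at one hospital department, "between July and December 2018". No matching, covariate adjustment or recording of draw time is described.

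**The concern.** A cycle-day rule has an obvious reason to be confined to controls, because women with POI may have no regular cycle to date from. A clock-time rule has no such reason, yet it appears only for controls. On a literal reading, one side of the primary comparison is held to a single hour and the other is left open.

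The groups are not randomised and neither named test carries covariates. If POI women were drawn at other hours, and if endocan moved with time of day, the resulting shift would be added to the difference in group means and could not be told apart from an effect of POI. It could create a false difference or hide a true one.

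**Working it through.** **The text.** Set side by side, the three timing statements do different jobs. The first covers all women and fixes the occasion (enrolment). The second fixes the cycle phase for controls, with the hour as its closing phrase. The third contrasts the POI group on the repeat interval, not on the hour. The clotting, centrifugation, storage and assay steps that follow are given without distinction by group. The text therefore leaves the POI hour unstated; it does not state a different one.

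**What a bias would require.** Two links must both hold:

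1. POI draws fell outside 08:00-09:00. The document does not say so.
2. Endocan differs by time of day. The document does not say so, and gives no endocan SD.

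**The plan's own figure.** There is none for draw time. The required total of 72 offers only a scale. It cannot be rebuilt forward, because no effect size or SD is given. Working back from 36 per group, assuming equal groups and a two-sided test at 0.05 with 80% power, (1.960 + 0.842) × √(2/36) = 0.66 SD, or 0.67 SD with the t distribution.

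**What would follow if both links held.** The group sizes (38 and 39) and alpha (0.05) are from the document. The off-window shares and the effects per sample are assumptions.

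- Shift in the POI mean = share of POI draws off-window × effect per off-window sample.
- Standard error of the difference, in SD units = √(1/38 + 1/39) = 0.228, with 75 degrees of freedom.
- False-positive rate = probability that a noncentral t, with noncentrality shift/0.228, exceeds the two-sided 5% limits.

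| Share off-window | Effect per sample | Shift | False-positive rate |
|---|---|---|---|
| none | any | 0 | 5.0% |
| 0.25 | 0.1 to 0.3 SD | 0.025 to 0.075 SD | 5.1% to 6.2% |
| 0.50 | 0.1 to 0.3 SD | 0.05 to 0.15 SD | 5.5% to 10.0% |
| 1.00 | 0.1 to 0.3 SD | 0.10 to 0.30 SD | 7.2% to 25.5% |

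Any bias of the same size, from any cause, would give the same rates. The table adds no evidence that draw time is such a cause.

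**Would a further analysis help?** The natural candidate limits the POI group to women drawn inside the window. It needs recorded draw times, which the document does not mention. It also costs precision. The 95% interval half-width is the t quantile × √(1/n₁ + 1/n₂): 0.454 SD for 38 versus 39, 0.560 SD for 19 versus 39, and 0.713 SD for 10 versus 39 (the counts 19 and 10 are assumed). An interval that wide would rarely settle whether a shift of 0.1 to 0.3 SD was present, and the women kept would be selected by draw time.

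**The case for a change.** The strongest case for a change is that the plan chose to standardise the hour in one group and gives no reason for leaving it open in the other. Section 5 counts the absence of treatments that might affect endocan as a strength, so control of outside influences on the measurement is one of the study's own aims. A common window would need no knowledge of whether endocan varies through the day, and it would cost one sentence, with no added visits or assays.

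Part of this stands. The document does not show whether draw time was the same in both groups, and a reader of the results may fairly ask. It does not carry as far as a change to the plan. The joint enrolment sentence and the single department make brevity a plausible explanation of the silence. The document is dated July 2018, yet it reports the enrolment of 77 women and the collection of samples mostly in the past tense. If that tense is right, a rule for POI draws would come too late. The wider absence of covariate adjustment is a separate matter, and draw time is only a speculative instance of it.

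**Conclusion.** No change to the plan follows. The hour is stated for controls and unstated for POI women; that is a missing detail in a very short document, not a rule shown to give a wrong or worse result. The bias has no size that the document can support: it is zero if either link fails, and the illustrative rates rest wholly on assumed shares and effects.

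The conclusion rests on reading the POI silence as brevity, which the text permits but does not prove. What remains is a reporting matter: the methods section of the study report can say whether POI samples were taken in the same hour and, if they were not, give the draw times where recorded or name unmatched timing as a limitation. Clear evidence that POI draws were scheduled at other hours, together with evidence that endocan varies by hour, would change this view. The document contains neither.

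### Does the repeat sampling in the POI group leave the primary endocan value undefined?

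*Combined protocol and SAP*

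**What the plan says.** Section 3 (Outcome Measures) opens with a rule for both groups: "At enrolment, all patients underwent vaginal ultrasonography for the assessment of antral follicle count (AFC) and venous blood sample from the antecubital veins". The analytes listed are endocan, FSH, E2, AMH and a blood count. Group-specific sentences follow:

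- Controls, timing: "venous blood samples and AFC were collected during the early follicular phase of the menstrual cycle (2nd to 5th days) in the morning", with a window of 08:00 to 09:00.
- POI group: "In the POI group, measurements were repeated with 4-week intervals".
- AMH: "AMH was not measured in the control group".

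The duration variable for the secondary endpoint is also defined there: "We defined that POI period is a time from diagnosis to admission".

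Section 4 (Endpoints of the study) states: "The primary endpoint in this analysis was to compare endocan levels in POI group and control group". The secondary endpoint relates endocan to POI duration within the POI group, and the tertiary endpoint compares endocan by birth history in both groups. None of the three carries a time point.

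Section 2 (Baseline Characteristics) gives the sample size in women: "the total number of individuals required to find a statistically significant effect size expectation was calculated as 72", at alpha 0.05 and power 0.80. For two-group comparisons of numerical variables it says that Student's "t-test (for normal data) or the Mann-Whitney U test (for non-normal data) was performed". It names no repeated-measures method and no averaging rule.

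**The concern.** Three features of section 3 invite the question.

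1. The rule for everyone and the sentences after it do not match. AMH is listed for all women and then excluded for controls. The control draw is tied to particular cycle days and an hour, whereas no hour is given for the POI group.
2. The sentence on repeats comes after a list that contains endocan and uses an unrestricted noun. Taken literally, a POI woman could have several endocan values, and the endpoint does not say which one counts.
3. POI duration stops at admission, so if admission means study entry, a later endocan value would postdate the duration it is set against.

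What would be at stake is the primary test. The t-test and the Mann-Whitney test both need independent observations. Entering several values per POI woman as if they came from different women would understate the standard error and inflate the false-positive rate. Choosing among a first, a second and a mean value after seeing the data would also inflate it.

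**Working it through.** **Inputs.** From section 1: 38 POI women and 39 controls. From section 2: 72 individuals, alpha 0.05, power 0.80. Not in the document and therefore assumed: a two-sided test, equal groups for the 72, two endocan values per POI woman where repeats are considered, and a within-woman correlation ρ of 0.5 to 0.9.

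**The plan's own figure.** The 72 cannot be derived forwards, because no effect size or SD is given. Solved backwards at 36 per group, the normal approximation gives d = (1.960 + 0.842) × √(2/36) = 2.802 × 0.2357 = 0.660. The exact t-test calculation gives d = 0.670, and putting 0.67 back in returns 72. If the test were one-sided, the exact value would be about 0.59. Nothing shows the 72 to be wrong.

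**One enrolment value per woman.** At d = 0.670 with 38 against 39, t-test power is 0.826. Simulated type I error under the null is 5.0–5.2% for the t-test and 4.9–5.0% for Mann-Whitney, which is 5% apart from simulation noise.

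**Two POI values per woman, pooled as independent.** This makes 2 × 38 + 39 = 115 values from 77 women. In units of the between-value variance:

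- True variance of the difference: [(1 + ρ)/2]/38 + 1/39.
- Variance the naive test assumes: 1/76 + 1/39 = 0.0388.
- Actual alpha: 2 × [1 − Φ(1.960 / √(true/naive))].

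| ρ | True variance | √(true/naive) | Actual alpha |
|---|---|---|---|
| 0.5 | 0.0454 | 1.081 | 7.0% |
| 0.7 | 0.0480 | 1.112 | 7.8% |
| 0.9 | 0.0506 | 1.142 | 8.6% |

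Simulation over the same range of ρ agrees to within about half a percentage point: 6.7–8.9% for the t-test and 6.4–8.6% for Mann-Whitney. Taking the smallest t-test p-value among first, second and mean gives about 8.1% at ρ = 0.5 and 6.4% at ρ = 0.9.

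**Which case does the text describe?** Side by side:

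- Section 3 puts endocan in the enrolment sample for both groups. To repeat a measurement presupposes a first one, so the sentence on repeats adds to the enrolment sample and does not replace it.
- Section 2 counts individuals, not samples, in its calculation for endocan.
- The tests named for comparing two groups take one value per woman.
- No sentence says that endocan was among the repeats, that values were pooled, or that one was chosen from several.
- Controls have a single described draw, so the like-for-like counterpart in the POI group is the enrolment draw.

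These point the same way, to the first case.

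**The mismatched sentences.** AMH for all women, then not for controls, reads as a general list followed by a stated exception, and the reader knows what was done. AMH appears in none of the three endpoints. The control timing says when the enrolment draw was taken and contradicts nothing if controls were sampled on entry. The document does not show that POI draws fell outside 08:00–09:00, nor that endocan varies by hour.

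**The case for a change.** The strongest reply is that no sentence ties the endpoint to the enrolment sample, that this is the sole primary outcome, and that naming the value would take one line and cost no power. If the reading is obvious, stating it is free. Unnamed values are also where selective reporting can enter, and the inflation calculated above is real for anyone who pools or picks.

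Part of this stands. The document is silent on what was repeated and how often, and a careful editor would add the line and limit AMH to the POI group. What does not stand is the step from silence to a defect in the analysis. The inflation needs endocan to have been repeated and the values to have been pooled or selected, and the document describes neither. Its size also rests on an assumed number of repeats and an assumed correlation.

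Nor is the enrolment value the only valid choice. A mean per POI woman would keep the observations independent, with power of 0.85–0.90 against 0.84 for a single value (normal approximation, d = 0.67, two values, ρ from 0.9 down to 0.3). The duration point adds nothing separate: relating duration at admission to a later measurement is not an error in itself, and the document does not link admission to enrolment. A sensitivity analysis by time of day would address a bias for which there is no evidence here.

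**Conclusion.** The concern does not call for a change. Followed as written, the plan yields one enrolment endocan value per woman, a t-test or Mann-Whitney test at its nominal 5%, and about 83% t-test power for a difference of 0.67 SD, given a two-sided test and equal groups behind the 72. The silence about which POI measurements were repeated is a gap that an analyst fills sensibly from the rest of the text. The AMH mismatch is a clerical slip outside every endpoint, and the control-timing sentence is a specification rather than a conflict. The 7.0–8.6% error rate illustrates an analysis that nobody has described and is not an estimate of harm in this study. The conclusion would need revisiting only if endocan proved to have been repeated and more than one value per woman had been used as independent data, or one had been selected after the results were seen.
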